### D3. Statistical Considerations

#### re: Specific Aim 1

With 20 subjects per group and assuming a two-sided alpha level of 0.05, there would be approximately 80% power to detect a 0.89 SD difference in progesterone or estrogen levels between PCOS women without and PCOS women with OSA. These values are derived from data obtained in a group of 10 PCOS women without OSA. Using the SD from the preliminary data, this study would be powered to detect a 42% difference in hormone levels between groups.

46 subjects will need to be enrolled for this Aim in order to ensure a sample size of 20 in the group of PCOS women without OSA; this figure of 46 subjects is based on an estimated 55% prevalence of OSA among PCOS women as shown in Preliminary Studies.

Progesterone and estrogen levels will be compared between the two groups using a two sample *t* test. A log transformation of the data will be performed if there is evidence of non-normality. Statistical correction will be made for multiple comparisons between groups.

#### re: Specific Aims 2 and 3

The PCOS women with OSA studied in Aim 1 plus additionally enrolled PCOS women with OSA (for a total of 60 subjects) will be randomized in a ratio of 2:1 to participate in Aim 2 (n=40) or Aim 3 (n=20). Block randomization will be performed using computer-generated random numbers.

#### • Specific Aim 2

For this Aim, there are three time points of interest: baseline (T1), six weeks after administration of depot leuprolide (T2), and at the end of study after receiving six weeks of either estrogen or progesterone

(T3). Treatment assignment to either estrogen (n=20) or progesterone (n=20) will be randomized using computer-generated random numbers.

If the variance in AHI is denoted by  $\sigma^2$  and the correlation between pre- and post-treatment AHI by  $r$ , then the variance of the change in AHI is given by  $2\sigma^2(1-r)$ . With 20 subjects per group and assuming a two-sided alpha level of 0.05, the **Table D3-1** below lists the difference in AHI change detectable between the two treatment groups with 80% power for varying values of  $r$ .

**Table D3-1. Difference in AHI change detectable between the two treatment groups with 80% power for varying values of  $r$ .**

$r$	Effect Size	Difference Detectable with $\sigma = 8$
0.25	$1.08\sigma$	8.6
0.50	$0.89\sigma$	7.1
0.75	$0.63\sigma$	5.0
0.90	$0.40\sigma$	3.2

Polysomnography results in a group of 17 PCOS women with OSA (defined by a total AHI  $\geq 10$ ) indicate that the mean AHI was  $18.4 \pm 8$  (Mean  $\pm$  SD). Using the SD from these preliminary data, for example, the present study would be powered to detect a difference of  $0.63 \times 8 = 5.04$  if the correlation is 0.75 (see **Table D3-1**). This would be equivalent to a mean change in AHI of 9.2 (a 50% decrease from baseline assuming a baseline level of 18.4) in the progesterone treated group versus a mean change of 4.2 (23% decrease from baseline assuming a baseline level of 18.4) in the estrogen treated group. The change in AHI ( $T_3 - T_1$ ) will be compared between the two groups using a two sample  $t$  test. This would amount to performing repeated measures analysis of variance on AHI and testing for group (progesterone vs. estrogen), time (pre- vs. post-treatment), and group by time interaction effects. The analysis will be performed both ways. Additionally, testosterone, estrogen, and progesterone levels at time T2 will be compared to the levels at T1 using a paired  $t$  test.

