Both progesterone and estrogen reportedly "protect" against the development of OSA (17, 18) (19-24) (25), and levels of these sex steroids are typically low in PCOS relative to those in normal cycling women. **Thus, we will test the hypothesis that circulating progesterone and estrogen levels are significant determinants in the development of OSA among hyperandrogenic women with PCOS. Using a novel paradigm that permits us to independently modulate sex steroid concentrations, we will be able to address the specific and independent effects of progesterone and estrogen in the pathogenesis of OSA among women with PCOS.**

OSA appears to be an underrecognized, yet significant factor in the pathogenesis of metabolic derangements in PCOS. In a recent study, we showed that measures of insulin resistance and glucose tolerance in PCOS women are strongly predicted by the severity of OSA (15). These intriguing findings suggest that there may be two "subtypes" of women with PCOS, i.e. those with and those without OSA, and that these two subtypes may be associated with distinct metabolic and endocrine alterations. PCOS women with OSA may be at much higher risk for diabetes and cardiovascular disease than PCOS women without OSA and may benefit from therapeutic interventions targeted to decrease the severity of OSA. **Thus, a major goal of the present project is to contrast the metabolic and hormonal features of these two subtypes of PCOS, explore causative mechanisms for the high prevalence of OSA in PCOS, and test the hypothesis that continuous positive airway pressure (CPAP) treatment may decrease the risk of diabetes and other cardiovascular and metabolic abnormalities in PCOS women with OSA.**

**Specific Aim 1. To determine if women with PCOS who have OSA differ from those without OSA as a consequence of differences in circulating concentrations of the sex-steroids estrogen and progesterone.** We hypothesize that in comparison to PCOS women without OSA, those who have OSA will have lower circulating levels of estradiol, progesterone, or both estradiol and progesterone at baseline. We will further test our hypothesis by comparing stimulated steroid levels in these two groups. Specifically,

we will compare the ovarian steroidogenic response to a single dose of the GnRH agonist leuprolide in PCOS women with and those without OSA. Developed by our group, the GnRH agonist test has become a novel method to assess ovarian steroidogenic function.

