## D2. Screening and Specific Aim 1 Procedures

46 subjects will need to be enrolled in Specific Aim 1 in order to ensure a sample size of 20 in the group of PCOS women without OSA; this figure of 46 subjects is based on an estimated 55% prevalence of OSA among PCOS women as shown in Preliminary Studies. This calculation accounts for the effects of expected dropouts from the study. The primary outcome measures for this Aim are the differences in progesterone and estrogen concentrations between groups.

[figure not shown]
Following an initial phone screening, eligible subjects will be admitted to the GCRC in the early evening and will undergo the following screening process as described in Figure D2-1, below.

**N.B. THE SCREENING PROTOCOL DETAILED BELOW WILL PERTAIN TO ALL SPECIFIC AIMS. BASED UPON THE RESULTS OF THIS SCREENING, SUBJECTS WILL BE CLASSIFIED AS EITHER OSA NEGATIVE, IN WHICH CASE THE**

EVALUATION IS COMPLETED, OR WILL BE CLASSIFIED AS **OSA POSITIVE**. OSA POSITIVE SUBJECTS WILL THEN BE GIVEN THE OPTION TO ENTER INTO THE PROTOCOLS DETAILED IN SPECIFIC AIM 2 OR SPECIFIC AIM 3. SUBJECTS WILL BE INFORMED THAT IF THEY CHOOSE TO CONTINUE INTO AIM 2 OR AIM 3, THEY WILL BE RANDOMLY ASSIGNED USING A RANDOMIZATION SCHEDULE PREPARED BY THE GCRC BIOSTATISTICIAN, DR. [name]. SUBJECTS RANDOMLY ASSIGNED TO SPECIFIC AIM 2 WILL ALSO BE INFORMED THAT FURTHER RANDOMIZATION WILL OCCUR TO ONE OF TWO TREATMENTS, AS DETAILED BELOW.

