**Table D3-2. Cortisol change detectable with 80% power for varying values of  $r$ .**

$r$	Effect Size	Difference Detectable with $\sigma = 2.2$
0.25	$0.77\sigma$	1.7
0.50	$0.63\sigma$	1.4
0.75	$0.44\sigma$	1.0
0.90	$0.28\sigma$	0.6

Preliminary data in a small group of OSA+ PCOS subjects indicate that the mean cortisol level was  $10.2 \pm 2.2$  (Mean  $\pm$  SD). Using the SD from the preliminary data, for example, this study would be powered to detect a difference of  $0.63 \times 2.2 = 1.4$  if the correlation is 0.50 (see **Table 2**).

Cortisol levels at time T2 will be compared to the levels at T1 using a paired  $t$  test. Additionally, the association between the changes ( $T_2 - T_1$ ) in cortisol and in total AHI with treatment will be assessed using Pearson correlation coefficients or Spearman rank correlation coefficients, as appropriate.

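### Aim 1's 80% power is computed at an uncorrected two-sided 0.05, but the same subsection promises a multiplicity correction without naming its method or family

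*Combined protocol and SAP*

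**What the plan says.** Section D3 (Statistical Considerations, Specific Aim 1) gives the power basis: "With 20 subjects per group and assuming a two-sided alpha level of 0.05, there would be approximately 80% power to detect a 0.89 SD difference". The comparison is of either hormone, progesterone or estrogen, between PCOS women with and without OSA. Using an SD from 10 women without OSA, it translates this into a 42% difference in hormone levels. On the analysis it says: "Progesterone and estrogen levels will be compared between the two groups using a two sample" *t* test, with a log transformation if needed, and then: "Statistical correction will be made for multiple comparisons between groups". It gives no method, list of comparisons or adjusted alpha.

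Section D2 makes both hormones primary: "The primary outcome measures for this Aim are the differences in progesterone and estrogen concentrations between groups". Section A states the Aim 1 hypothesis as either-or-both: "those who have OSA will have lower circulating levels of estradiol, progesterone, or both estradiol and progesterone at baseline". It adds a comparison of stimulated steroid levels after leuprolide.

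For Aim 3, Table D3-2 is titled "Cortisol change detectable with 80% power for varying values of" *r*, with 20 subjects. The text below it says: "Using the SD from the preliminary data, for example, this study would be powered to detect a difference of" 0.63 × 2.2 = 1.4 at a correlation of 0.50. The analysis is: "Cortisol levels at time T2 will be compared to the levels at T1 using a paired" *t* test.

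**The concern.** If a positive result on either of two primary hormones supports the hypothesis, testing each at 0.05 inflates the chance of a false claim. With independent tests it is 1 − 0.95² = 9.75%. The plan recognises this by promising a correction, but its power statement ignores that correction. A reader would take 80% as the power of the planned test for each hormone, and it is not.

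The open method and family matter at least as much. Sections D2 and D3 say estrogen, section A says estradiol, and Table D1 lists estradiol, estrone and progesterone. Stimulated levels could also be counted. Bonferroni appears only in the footnote on multiple comparisons to the preliminary OSA tables in C4, and Tukey only in the footnote to Table C2-1. Neither is assigned to Aim 1. The significance threshold for a primary outcome could therefore be fixed after the results are known.

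Table D3-2 raises a separate, smaller point: its entries are labelled 80% power but ignore the 19 degrees of freedom of the planned test.

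**Working it through.** **Inputs.** From D3, Aim 1: 20 per group, two-sided alpha 0.05, difference 0.89 SD (so SD = 1), two-sample *t* test. From D2: 46 enrolled at 55% OSA prevalence, which gives 46 × 0.45 = 20.7 without OSA and 46 × 0.55 = 25.3 with OSA. Table D1 lists 23 and 23. Assumption, because the plan is silent: Bonferroni over the two hormones, so alpha = 0.05/2 = 0.025 each. This is the smallest family the text supports.

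**The plan's figure reproduced.** The noncentrality is 0.89 × √(20/2) = 2.814. By the normal approximation, power = Φ(2.814 − 1.960) = Φ(0.854) = 80.4%. The detectable difference is (1.960 + 0.842) × √(2/20) = 0.886 SD, which matches the printed 0.89. The noncentral *t* gives 78.3%, still a fair reading of approximately 80%. A one-sided test would give about 87–88% and does not match. The printed figure therefore rests on the undivided 0.05.

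**Per-hormone power at 0.89 SD (noncentral *t*).**

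| Analysed | alpha 0.05 | alpha 0.025 | SD detectable with 80% power at 0.025 |
|---|---|---|---|
| 20 and 20 | 78.3% | 68.4% | 1.009 |
| 20 and 25 | 82.6% | 73.8% | 0.953 |
| 23 and 23 | 83.9% | 75.5% | 0.936 |

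With three hormones (alpha 0.0167) and 20 per group, power is 62.3%. Keeping 0.89 SD with at least 80% power at 0.025 takes 26 per group (81.2%).

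**On the percentage scale.** The implied SD/mean is 0.42/0.89 = 0.472. Then 1.009 × 0.472 = 47.6% and 0.936 × 0.472 = 44.2%, against the printed 42%. This holds only on the untransformed scale.

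**Other readings** (simulation, 100,000 trials, 20 per group):

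- Both hormones differ by 0.89 SD, at least one p < 0.025: 90%, 87%, 83% and 79% at between-hormone correlations of 0, 0.25, 0.5 and 0.75.
- Holm, per hormone, both differ: 74–75%.
- Only one hormone differs: about 69% under Bonferroni or Holm.

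**Table D3-2.** With n = 20 the normal-based standardised change is (1.960 + 0.842)/√20 = 0.6265. Multiplying by √(2(1 − r)) gives 0.767, 0.626, 0.443 and 0.280, which are the printed effect sizes. Under the planned paired *t* test, the standardised change for 80% power is 0.6604, larger by 0.6604/0.6265 = 1.054.

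| r | Printed (σ) | Its power, paired *t* | 80% value (σ) | × 2.2 | Printed × 2.2 |
|---|---|---|---|---|---|
| 0.25 | 0.77 | 76.0% | 0.809 | 1.78 | 1.7 |
| 0.50 | 0.63 | 76.2% | 0.660 | 1.45 | 1.4 |
| 0.75 | 0.44 | 75.2% | 0.467 | 1.03 | 1.0 |
| 0.90 | 0.28 | 75.7% | 0.295 | 0.65 | 0.6 |

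The same check on Table D3-1 (Aim 2, 38 degrees of freedom) gives 77.6–78.7%, close enough to stand.

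**The case against.** The strongest reply is that nothing was miscalculated: 80% is right for the alpha stated, and any corrected figure depends on a method and family the plan does not give. That is true, and it limits what can be said about size. It does not remove the mismatch. The correction sentence closes the paragraph on the progesterone and estrogen *t* test and exempts neither hormone. It could be read as aimed at other comparisons, but the text does not say so.

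Second, the hypothesis needs only one hormone, and power for at least one is 79–90% if both differ by 0.89 SD. This also stands, but the plan does not claim that quantity, and it drops to about 69% if only one hormone differs.

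Third, 20 per group is a floor, and the enrolled numbers are larger. With them power is about 74–75%, still short of 80%. D2 also says the 46 already allows for dropouts, so 20 analysed is a realistic case and is the plan's own power basis.

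Fourth, the practical shift is modest. The SD comes from 10 women. A normal-theory 95% interval for it spans 0.69 to 1.83 times the estimate, so the 42% could be anywhere from 42 × 0.69 = 29% to 42 × 1.83 = 77%. A move to 44–48% lies well inside that range. This is a good reason not to ask for more subjects, but it does not justify leaving the decision rule open.

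Finally, Table D3-2 is a minor matter. The preliminary cortisol fall in C8 is 10.2 − 7.7 = 2.5, larger than every entry, so Aim 3 is not threatened.

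**Conclusion.** The concern holds. The Aim 1 power and detectable difference are computed for an uncorrected test, while the plan commits to a corrected one and specifies neither method nor family. That mismatch is certain from the text. Its size is conditional: under Bonferroni over two hormones, per-hormone power at 0.89 SD is 68% (20 per group) to 75% (23 per group), roughly 8 to 10 points below the same t-test calculation at 0.05. It is 62% with three hormones and 20 per group. Holm recovers part of the loss if both hormones truly differ. The matter is worth correcting because it concerns the decision rule for the primary outcomes, but it does not undermine the design. In Table D3-2 the printed effect sizes carry 75–76% power rather than 80%, and two of the four cortisol values change at one decimal. That is a correction of printed figures only.

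**What to change.** For Aim 1, add two or three sentences to D3 that:

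- name the correction method;
- list the hormones and time points in its family, settling whether estrogen means estradiol, estrone or both, and whether stimulated levels are included;
- say whether the power target is per hormone or for at least one hormone;
- restate power or the detectable difference at the resulting alpha. For Bonferroni over two hormones with 20 per group, this is about 68% for 0.89 SD, or about 1.0 SD (roughly 48%) at 80% power. With 23 per group it is about 75%, or 0.94 SD (roughly 44%).

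For Aim 3, replace the Table D3-2 effect sizes with 0.81, 0.66, 0.47 and 0.30 σ, and the cortisol values with 1.8, 1.5, 1.0 and 0.6. The worked example becomes 0.66 × 2.2 = 1.5. Compute the last row from the unrounded 0.295 (0.295 × 2.2 = 0.65, printed as 0.6 because the unrounded product is 0.6498), or print 0.295, since 0.30 × 2.2 would round to 0.7. Table D3-1 can stay.

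The cost is a few sentences, one small table and one worked example. The stated Aim 1 sensitivity becomes less favourable, and enrolment does not change.

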**At 15:50, a GnRH agonist test will be performed, as depicted in FIGURE D2-3 below.**

At 15:50, a 15cc blood sample for LH, FSH, estradiol, estrone, total and free testosterone, progesterone, 17-hydroxyprogesterone, and androstenedione will be obtained. At 15:59, a 5 cc blood sample will be taken for LH and FSH. At 16:00, leuprolide acetate 10 µg/kg will be given as a single subcutaneous injection. At 16:30, 17:00 and 20:00, 5 cc samples will be obtained for LH and FSH. A 15 cc sample will be obtained for estradiol, estrone, total and free testosterone, progesterone, 17-hydroxyprogesterone, and androstenedione after 16, 20, 24 hours GnRHa administration, i.e. at 8:00, 12:00 and 16:00.

As depicted in Figure D1-1, it is at this point that subjects will have completed the Screening and Specific Aim 1 Procedures. Details of procedures for subjects randomized into Specific Aim 2 or Specific Aim 3 are provided below.

### D3. Detail of methods pertaining to Specific Aims 2 and 3

The PCOS women with OSA studied in Aim 1 plus additionally enrolled PCOS women with OSA (for a total of 60 subjects) will be randomized in a ratio of 2:1 to participate in Aim 2 (n=40) or Aim 3 (n=20). Block randomization will be performed using computer-generated random numbers. The primary outcomes measure for Aim 2 is the AHI difference pre- and post-interventions, as detail in Section D3; the primary outcomes measure for Aim 3 is the change in 24 hr cortisol concentration pre- vs post-CPAP

Subjects randomized to Specific Aim 2 will have suppression of endogenous LH secretion, and thus ovarian sex-steroid production, by administration of a single intramuscular dose (11.25 mg) of the GnRH agonist depot leuprolide. Leuprolide is a synthetic nonapeptide analog of naturally occurring gonadotropin-releasing hormone (GnRH). The analog possesses greater potency than the natural hormone. When the depot form of leuprolide is administered at a dose of 11.25 mg, there is prolonged (3 month) suppression of pituitary gonadotropin levels and ovarian steroid levels as documented in the literature (115) and exemplified in Preliminary Studies. Six-weeks after administration, subjects will return to the GCRC for repeated evaluation, identical to that conducted at Baseline under Specific Aim 1.

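### Aim 1 is sized at 20 or 23 women with OSA, and about 35 to 37 further untreated OSA-positive baselines appear not to be used in its hormone comparison

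*Combined protocol and SAP*

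**What the plan says.** All references are to the combined protocol and SAP.

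- **Aim 1 size.** D3, Statistical Considerations, gives the power statement: "With 20 subjects per group and assuming a two-sided alpha level of 0.05, there would be approximately 80% power to detect a 0.89 SD difference". It converts this to the percent scale: "this study would be powered to detect a 42% difference in hormone levels between groups". Enrolment is set at 46 so that the group without OSA reaches 20, at an assumed OSA prevalence of 55%. Table D1 shows 23 women in each Aim 1 group.
- **Aims 2 and 3.** D3, Detail of methods, describes the population as "The PCOS women with OSA studied in Aim 1 plus additionally enrolled PCOS women with OSA (for a total of 60 subjects"), randomized 2:1 to Aim 2 (40) or Aim 3 (20). D3, Statistical Considerations, repeats this.
- **Shared baseline.** D2 states: "THE SCREENING PROTOCOL DETAILED BELOW WILL PERTAIN TO ALL SPECIFIC AIMS". The text that closes the description of the GnRH agonist test places the Screening and Aim 1 procedures before any Aim 2 or Aim 3 procedure. Six weeks after depot leuprolide, Aim 2 "subjects will return to the GCRC for repeated evaluation, identical to that conducted at Baseline under Specific Aim 1". Aim 3 repeats the same study outline after CPAP. The Aim 2 analysis compares testosterone, estrogen and progesterone at T2 with their T1 values.
- **Aim 1 analysis.** A two-sample t test, log-transformed if the data look non-normal, with a correction for multiple comparisons whose method is not given.

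No section adds the additional women's baselines to the Aim 1 comparison, and none expressly keeps them out.

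**The concern.** Aim 1 tests the project's central hypothesis, that women with PCOS and OSA have lower estradiol, progesterone or both. The group that is hard to fill is women without OSA. More women with OSA are being enrolled in any case, and before treatment they appear to have the hormone measurements that Aim 1 needs. If those values are not used, the Aim 1 primary comparison is less precise than the study's own data allow. If the question stays open until data are in hand, the choice of analysis set for a primary outcome becomes post hoc.

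**Working it through.** **Inputs.** Two-sided alpha 0.05, difference 0.89 SD, 42% conversion, 46 women, 55% prevalence and 60 OSA-positive women (all D3, Statistical Considerations); 23 and 23 (Table D1).

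**1. The plan's figure.** With SD = 1 and 20 per group, the normal approximation gives a detectable difference of (1.960 + 0.842) × sqrt(1/20 + 1/20) = 0.886 SD and 80.4% power at 0.89 SD. The noncentral t gives 78.3% power and 0.91 SD. The stated figure reproduces.

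**2. What the plan's own enrolment implies.** 46 × 0.55 = 25.3 women with OSA and 46 × 0.45 = 20.7 without. The starting point is therefore about 20 vs 25, or 23 vs 23 by Table D1. The additional OSA-positive women number 60 − 25 = 35 or 60 − 23 = 37. The 55% comes from a cut-off of AHI ≥ 5 (C4), whereas D2 defines OSA as AHI > 15, so the split is approximate.

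**3. Effect of including them.** SE = sqrt(1/n1 + 1/n2) in SD units. Power and detectable difference are from the noncentral t with pooled variance. Percent = 42 × d/0.89.

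| No OSA vs OSA | SE | Power at 0.89 SD | Detectable, 80% power | Percent |
|---|---|---|---|---|
| 20 vs 25 | 0.300 | 82.6% | 0.86 SD | 41% |
| 20 vs 60 | 0.258 | 92.6% | 0.73 SD | 35% |
| 23 vs 23 | 0.295 | 83.9% | 0.845 SD | 40% |
| 23 vs 60 | 0.245 | 94.8% | 0.70 SD | 33% |

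The SE falls by 1 − 0.258/0.300 = 14%, or by 1 − 0.245/0.295 = 17%. With 10% loss among the 60 (20 vs 54), power is 91.8%.

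**4. Welch test.** With equal SDs, the Welch degrees of freedom at 20 vs 60 are about 33. Power is 92% and the detectable difference 0.75 SD. At 23 vs 60 they are 94% and 0.70 SD.

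**5. Multiplicity.** The correction is not specified. If it were Bonferroni over two hormones (assumption, alpha 0.025), pooled-variance power would go from 73.8% (20 vs 25) to 87.5% (20 vs 60), or from 75.5% (23 vs 23) to 90.8% (23 vs 60).

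**6. Unequal SDs.** The plan's SD comes from 10 women without OSA, and none is given for women with OSA. Suppose the group without OSA had 1.5 times the SD of the other (assumption), with the difference fixed at 0.89 of the smaller SD. Welch power then goes from 60% (20 vs 25) to 66% (20 vs 60), or from 64% (23 vs 23) to 72% (23 vs 60). With the larger SD in the OSA group instead, it goes from 64% to 84%, or from 64% to 87%.

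**The case against.** **The plan does not say that these women are left out.** Twenty per group is a planning number, the 46 is driven by the group without OSA, and nothing caps the OSA group. D2 can be read as taking every woman through the Aim 1 procedures first, so the additional women might already count. This stands in part: exclusion is an inference. But the plan separates women studied in Aim 1 from those enrolled additionally, and Table D1 sizes the Aim 1 OSA group at 23. The natural reading is two cohorts, and on either reading the analysis set is undefined.

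**A larger gain is tempting.** A reader might set 60 against the 20 in the power statement and infer 40 unused baselines, power rising from 78% to 93% and an SE 18% lower. The documents do not support that starting point, because the planned enrolment gives about 25 women with OSA, or 23 by Table D1.

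**Comparability.** In the 46-woman cohort both groups come from one concurrent intake. The additional women enrol for having OSA and agree to randomization. D5 promises one assay run per hormone only within a subject, so enrolment-period or assay drift could align with group. This stands. An analysis of the original cohort discloses the problem but, at about 20 vs 25, has limited ability to detect it.

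**The sampling is not certain.** Table D1 lists estradiol, estrone and progesterone once for Aim 1 and twice for Aim 2, which has three time points. That the additional women have the full baseline is pieced together from several sections and needs confirming.

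**Conclusion.** The point holds as an inexpensive gain in precision. The 20-per-group calculation is right on its own inputs and nothing in Aim 1 is invalid. A reader might infer that the plan discards these data or that Aim 1 is underpowered as designed. The first is not stated anywhere, and the plan meets its approximate 80% target at the unadjusted alpha.

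About 35 to 37 untreated OSA-positive baselines appear to be available but unused. Including them adds about 10 to 11 percentage points of power at 0.89 SD and lowers the SE by about 14% to 17%. The detectable difference falls from about 40% to 33-35% on the plan's conversion. This assumes equal SDs, alpha 0.05 before multiplicity correction, the planned numbers, and T1 sampling in the additional women that matches Aim 1. The 20 to 23 women without OSA limit the gain, and it shrinks if they are the more variable group.

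**What to change.** 1. Confirm that every additional OSA-positive woman has the same T1 estrogen and progesterone sampling as the Aim 1 women, and reconcile the test counts in Table D1.
2. If so, pre-specify the Aim 1 OSA group as all OSA-positive women with a completed T1 baseline (up to 60), compared with all OSA-negative completers by a Welch test.
3. Report the original 46-woman cohort alongside as a sensitivity analysis, and state that it can show but not rule out an enrolment-period or selection effect.
4. Restate the detectable difference for about 20 to 23 vs 60, with the multiplicity method named and a range for unequal SDs.

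The cost is analysis-plan wording. If step 1 is confirmed, no women, visits or assays are added. The price is unequal groups and some loss of concurrency between them.
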